#### 2.1.1.5 Visit windows

[figure not shown]
Visit-windows will be used for the data that is summarized by visit; these are based on the study evaluation schedule and comprise a set of days around the nominal visit day. For any assessment, there are the protocol defined scheduled visits around which visit windows were created to cover the complete range of days within the study. The visit windows are shown in [Table 2-2a](#) [REDACTED], which apply to measurements taken at every visit. For assessments collected less often, different visit windows will be applied as detailed below. When visit windows are used, all visits will be re-aligned, i.e., they will be mapped into one of the visit windows. E.g., if the Week 4 visit of a subject is delayed and occurs on Day 46 instead of on Day 29, say, then it will be re-aligned to visit window Week 8. In the case of major deviations from the visit schedule, or due to unscheduled visits, several assessments of a subject may fall in a particular visit window (either scheduled or unscheduled). Statistical approaches to handle multiple assessments in a given visit window are specified below. Of note, subjects are allowed to have gaps in visits.

**Table 2-2a      Assessment windows for scheduled visits**

| Analysis Visit | Week | Scheduled Day | Visit Window                                   |
|----------------|------|---------------|--|
| Baseline       | BSL  | 1             | -to Day 1
(-28 days to Day 1 for psoriasis) |
| Week 1         | 1    | 8             | Day 2-11                                       |
| Week 2         | 2    | 15            | Day 12-18                                      |
| Week 3         | 3    | 22            | Day 19-25                                      |
| Week 4         | 4    | 29            | Day 26-43                                      |
| Week 8         | 8    | 57            | Day 44-71                                      |
| Week 12 (EOI)  | 12   | 85            | Day 72-88                                      |
| Week 13        | 13   | 92            | Day 89-95                                      |
| Week 14        | 14   | 99            | Day 96-102                                     |
| Week 15        | 15   | 106           | Day 103-109                                    |
| Week 16        | 16   | 113           | Day 110-127                                    |

|                    |     |      |               |
|--------------------|-----|------|---------------|
| Week 20            | 20  | 141  | Day 128-155   |
| Week 24            | 24  | 169  | Day 156-183   |
| Week 28            | 28  | 197  | Day 184-211   |
| Week 32            | 32  | 225  | Day 212-239   |
| Week 36            | 36  | 253  | Day 240-267   |
| Week 40            | 40  | 281  | Day 268-295   |
| Week 44            | 44  | 309  | Day 296-323   |
| Week 48            | 48  | 337  | Day 324-351   |
| Week 52 (EOM)      | 52  | 365  | Day 352-407   |
| Week 64            | 64  | 449  | Day 408-491   |
| Week 76            | 76  | 533  | Day 492-575   |
| Week 88            | 88  | 617  | Day 576-673   |
| Week 104           | 104 | 729  | Day 674-771   |
| Week 116           | 116 | 813  | Day 772-855   |
| Week 128           | 128 | 897  | Day 856-939   |
| Week 140           | 140 | 981  | Day 940-1037  |
| Week 156           | 156 | 1093 | Day 1038-1135 |
| Week 168           | 168 | 1177 | Day 1136-1219 |
| Week 180           | 180 | 1261 | Day 1220-1303 |
| Week 192           | 192 | 1345 | Day 1304-1401 |
| Week 208           | 208 | 1457 | Day 1402-1499 |
| Week 220           | 220 | 1541 | Day 1500-1583 |
| Week 232           | 232 | 1625 | Day 1584-1639 |
| Week 236 (EOT)     | 236 | 1653 | Day 1640-1667 |
| Week 240 (F4)      | 240 | 1681 | Day 1668-1695 |
| Week 244 (F8)      | 244 | 1709 | Day 1696-1723 |
| Week 248 (F12)     | 248 | 1737 | Day 1724-1751 |
| Week 252 (F16 EOF) | 252 | 1765 | Day 1752-1779 |

EOI: End of Induction Period; EOM: End of Maintenance Period; EOT: End of Treatment; EOF: End of Follow-up

For parameters, which are not collected at every visit (e.g. weight), visit windows defined in the tables above will be combined. E.g., if a parameter is measured at Week 12 and Week 24 only, then Week 12 visit window will extend from Day 2 to Day 88 (combining Week 1 to Week 12 visit windows), Week 24 will extend from Day 89 to Day 183 (combining Week 13 to Week 24). If more than one assessment falls into the interval, then the rules defined in [Section 2.1.1.6](#) are applied.

Maintenance period visits will not be mapped into induction period, and induction period visits will not be mapped into maintenance period. For example, if a subject is coming late for the Week 12 visit (induction period), and the visit would fall into the Week 13 (maintenance period) visit window, then it would not be mapped to maintenance period for the analysis but will still be considered as part of induction period. Of note, for subjects who discontinue in induction/maintenance period, i.e. not moving into maintenance/extension period, measurements taken in follow-up period would still be considered for induction/maintenance period.

In addition, sensitivity analyses for PASI and IGA mod 2011 0/1 response parameters will be performed based on extended Week 12 visit window from Day 72 to Day 102. See [Section 4.1](#) for details.

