## Induction Epoch

The induction epoch is defined as randomization through Week 12 (prior to dose). In this epoch the study is both active and placebo-controlled and at its completion the primary endpoint is assessed (Week 12).

At the start of the induction epoch, eligible subjects will be randomized in a 1:1:1:1 ratio into one of four treatment groups (etanercept, secukinumab low dose group, secukinumab high dose group, or placebo group). The randomization will be stratified by age (<12 years or ≥12 years) and weight (<25, 25-≤50, ≥50) at randomization; Subjects randomized to the secukinumab treatment group will receive respective high and low doses according to their weight category. Subjects randomized to the placebo group will be pre-assigned to either the low- or high-dose group of secukinumab, at the Randomization visit, in case they are not achieving a PASI 75 response as assessed at Week 12. During the induction epoch, all subjects will be visiting the study site at Randomization and Weeks 1, 2, 3, 4, 8, and 12. The secukinumab and placebo treatment groups will receive s.c. study treatment and/or s.c. placebo weekly for four weeks (randomization and Weeks 1, 2, and 3) and then one dose of study treatment and/or placebo at

Weeks 4 and 8 (last dose during the induction epoch). Secukinumab will be administered at site. Subjects in the etanercept arm will receive weekly s.c. dose of 0.8 mg/kg (up to a maximum of 50 mg) of open-label etanercept. Etanercept will be administered at site during site visits and at home or at the site for the remaining weekly visits based on the visit schedule ([Table 6-1](#) and [Table 6-2](#)).

Assessments for the primary endpoint will be done at Week 12 for all treatment arms prior to the dose at Week 12.

For subjects who discontinue study treatment for any reason before the end of the induction epoch, an EOI Visit (Week 12 Visit) should be performed approximately four weeks after their last dose of study drug and then the subject will enter the post-treatment follow-up period and perform F4, F8, F12 and F16 visits. If subjects start another systemic anti psoriatic treatment during follow up, they do not need to continue with the remaining follow-up visits but they will be expected to return to site after the start of the systemic treatment and perform End of Follow-up (EOF) visit.

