#### **Suggested order of assessments:**

Suggested guidelines for conduct of the visit assessments are below:

- Subject to complete CDLQI at the study site prior to any study assessments
- Parent/custodian (or together with subject if subject is of 18 years of age or older) to complete childhood health assessment questionnaire, CHAQ©
- Efficacy assessor to complete efficacy assessments.
  1. IGA mod 2011 (all visits)
  2. PASI (all visits)
- Investigator to complete investigator assessments
  1. Review CDLQI and CHAQ data (at applicable visits)

2. Physical exam (at applicable visits)
  - All remaining study visit procedures (e.g., laboratory sample collection, vital signs measurements) must be completed prior to study treatment dosing.
  - Enter PASI data into the source data worksheets and perform calculations as needed BEFORE contacting IRT at randomization and Week 12 Visit.
  - Contact IRT to register the subject visit, as applicable
  - Administration of study treatment, as applicable

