### 1.1 Study design

This is a multicenter, randomized, double-blind, placebo-and active-controlled (etanercept in single blinded arm) study in pediatric subjects aged 6 years to less than 18 years with severe chronic plaque psoriasis. Approximately 160 subjects aged 6 years to <18 years will be enrolled, of which at least 30 pediatric subjects will be 6 years to <12 years old. In reality around 40-45 patients will be needed to meet the requirement of recruiting about 30% of subjects in the < 25kg weight group.

Subjects will be randomized using a 1:1:1:1 ratio into one of the treatment arms: secukinumab low dose, secukinumab high dose, etanercept or placebo. The randomization will be stratified by age (<12 years or ≥12 years) and weight (<25 kg, 25-<50 kg, ≥50kg) at randomization. Subjects randomized to the placebo group will be pre-assigned to either the low- or high-dose group of secukinumab, at the Randomization visit, in case they are not achieving a PASI 75 response as assessed at Week 12.

The study consists of 5 Epochs: screening (up to 4 weeks), induction (of 12 weeks), maintenance (of 40 weeks), extension treatment epoch (open-label of 184 weeks) and post-treatment follow-up epoch (of 16 weeks). The detailed information of the study design is described in [Figure 1-1](#).

**Figure 1-1** Study design

The following study periods will be considered for analysis:

- **Screening period** (before Randomization)
- **Induction period** (Randomization to Week 12 pre-dose), including follow-up period (F4, F8, F12 and F16 (EOF) visits) for prematurely discontinued subjects before Week 12 completion. For placebo PASI 75 responders at Week 12, subjects will enter follow-up period after Week 12, including the first visit F4 and four weeks later visit EOF at F8.
- **Maintenance period** (Week 12 dose to Week 52 pre-dose), including follow-up period (F4, F8, F12 and F16 visits) for prematurely discontinued subjects before Week 52 completion, and for etanercept patients with the completion of the maintenance epoch.
- **Extension period** (Week 52 dose until Week 236 (EOT)), including follow-up period (F4, F8, F12 and F16 visits) for prematurely discontinued subjects before Week 236 completion.
- **Entire treatment period** (Randomization to Week 236 (EOT)), for safety analysis, exposure including follow-up period up to last dose + 84 days.
- **Entire study period** (Randomization to end of study (EOS)), including follow-up period (F4, F8, F12 and F16 visits).

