## 2.6.4 Handling of missing values/censoring/discontinuations

The following imputation methods will apply to the missing data for analysis up to Week 52 including primary W12 analysis:

- Response variables based on PASI score and IGA mod 2011 categories will be imputed with multiple imputations (MI) method as primary imputation method. Multiple imputation (MI) is a simulation based approach where missing values are replaced by multiple Bayesian draws from the conditional distribution of missing data given the observed data and covariates, creating multiple completed data sets. These completed data sets can then be analyzed using standard methods. Within this analysis, the PASI score or

IGA mod 2011 categories will be imputed and response variables will be derived based on the imputed scores. In the multiple imputation analysis, the response status will be imputed based on the individual treatment arm information.

- (Pure) Non-responder imputation will be used as a sensitivity method: Missing values with respect to response variables based on PASI score and IGA mod 2011 categories will be imputed with non-response regardless to the reason for missing data. Subjects with missing baseline or those with all post-baseline missing will be imputed with non-response.

[REDACTED]

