### 4.1 Additional and data driven analysis

In addition to the planned analyses, the following additional analyses will be performed after the database lock of the Week 24 analysis.

#### Analyses using extended visit window for Week 12

Sensitivity analysis with extended Week 12 analysis visit window using MI and pure non-responder imputation for missing data will be performed (Week 12 visit window day 72-102, instead of day 72-88). Number and percentage of subjects with PASI 50, PASI 75, PASI 90, PASI 100 and IGA 0 or 1 response at Week 12 will be summarized. Moreover, an exact logistic regression will be fitted to compare AIN457 low and high dose groups to the controls. This additional analysis was driven by the review of data post Week 24 DBL. As a number of patients, delayed beyond Day 88 their Week 12 CRF visit, this analysis was done to have a better understanding of the impact of these delays.

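### PASI and IGA scores taken after a discontinued patient has started another systemic psoriasis drug count as the randomised arm's response, mainly in the Week 16 to Week 52 by-visit estimates

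*SAP*

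**What the plan says.** **Who is assessed after switching.** Under Protocol 3.1 (Induction Epoch), after early discontinuation "an EOI Visit (Week 12 Visit) should be performed approximately four weeks after their last dose of study drug". The patient then enters follow-up (F4 to F16). Patients who start another systemic anti-psoriatic drug in follow-up may skip the remaining visits, but "they will be expected to return to site after the start of the systemic treatment and perform End of Follow-up (EOF) visit". The Maintenance Epoch text repeats this rule, with the EOM visit in place of EOI. The suggested order of assessments in Protocol 6 has IGA and PASI at every visit, and Table 6-2 marks both in the follow-up columns.

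**Which period the score belongs to.** SAP 1.1 defines the induction period as "including follow-up period (F4, F8, F12 and F16 (EOF) visits) for prematurely discontinued subjects before Week 12 completion" and the maintenance period as "including follow-up period (F4, F8, F12 and F16 visits) for prematurely discontinued subjects before Week 52 completion". SAP 2.1.1.5 says the same for visit windows: "measurements taken in follow-up period would still be considered for induction/maintenance period".

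**Which value is used, and for which arm.** SAP Table 2-3 takes the value closest to the target day, whatever treatment the patient is then receiving. The FAS (SAP 2.2) analyses patients by randomised arm.

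**Missing data.** In SAP 2.6.4, MI is the primary method and fills missing scores. In the pure non-responder sensitivity analysis, missing responses are "imputed with non-response regardless to the reason for missing data". Neither rule addresses an observed score taken on another drug.

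**The concern.** Patients who stop for lack of effect are plausibly the ones most likely to start another systemic drug. If they improve on it, a failure of the assigned treatment is recorded as a response to that treatment. The named sensitivity method for missing data cannot show this, because the score is observed. The same score also enters the MI model, which is fitted by treatment group (SAP 5.1.2.3). It can therefore shape the imputed values for that patient's later visits and, to a lesser degree, for other patients in the arm.

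At stake is what the by-visit response rates mean. A reader of the Week 16 to Week 52 curves would take them as response on the assigned regimen.

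**Working it through.** **1. Plan's own figures.** SAP 3 assumes 40 per arm and Fisher's exact test at 1.25% one-sided. Full enumeration of the two binomials gives:

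| Endpoint | Placebo v secukinumab | Power, plan | Power, recomputed |
|---|---|---|---|
| PASI 75 | 10% v 65% | 99% | 99.9% |
| IGA 0 or 1 | 10% v 45% | 88% | 88.4% |
| PASI 90 | 8% v 39% | 82% | 82.1% |

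These figures reproduce and do not depend on this point.

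**2. Can a post-switch score reach the Week 12 window (Day 72-88)?** Nominal days are last dose + 28 (EOI), + 56 (F4), + 84 (F8).

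| Last dose | EOI | F4 | F8 | In Day 72-88 |
|---|---|---|---|---|
| Day 1 | 29 | 57 | 85 | F8 |
| Day 8 | 36 | 64 | 92 | none |
| Day 15 | 43 | 71 | 99 | none |
| Day 22 | 50 | 78 | 106 | F4 |
| Day 29 | 57 | 85 | 113 | F4 |
| Day 57 | 85 | 113 | 141 | EOI |

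The EOF visit triggered by a switch has no fixed day, so it can land in the window for any last dose up to Day 29. The Day 92 and Day 99 visits fall only in the sensitivity window ("Week 12 visit window day 72-102, instead of day 72-88"). After a last dose on Day 57, the EOI visit itself falls on target Day 85 and would normally precede any switch. Week 12 exposure is therefore confined, in practice, to patients who stop by about Week 4 and switch soon after.

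Example: a placebo patient has the last dose on Day 22 and EOI on Day 50 (Week 8 window, Day 44-71), starts a systemic drug, and has EOF on Day 80. Day 80 becomes the Week 12 value.

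**3. Maintenance.** The Week 52 window ends on Day 407. With the last dose at Weeks 12 to 36, every visit from EOM to F16 falls by then (Week 36: 253 + 140 = 393). With the last dose at Week 40, 44 or 48, visits up to F12, F8 and F4 respectively do (each Day 393).

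Example: a secukinumab patient has the last dose at Week 20 (Day 141) and EOM on Day 169 (Week 24 window), switches, and has EOF on Day 225. That is the Week 32 value (Day 212-239). Under pure non-responder imputation the missing Weeks 36 to 52 are non-response, so one visit is affected. Under MI those visits are imputed, and the Week 32 score can inform them.

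**4. Size.** One switched responder in 40 is 1/40 = 2.5 points. Let s be the share of an arm with a post-switch score in a window and q the response rate on the new drug. Compared with scoring these patients as non-responders, the arm's rate rises by s × q, and the secukinumab-minus-placebo difference changes by (s_secukinumab − s_placebo) × q. The documents give neither s nor q. For illustration, q = 54.7%, the etanercept PASI 75 rate quoted in Protocol 1.1.

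- One switcher in a window: 0.025 × 0.547 = 1.4 points expected, 2.5 if that patient responds.
- Four switchers (10%) all in one window: 0.10 × 0.547 = 5.5 points expected. Ten points would require all four to respond.
- Difference at Week 12: 10% in secukinumab only, +5.5; 10% in placebo only, −5.5; equal shares, 0.

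**5. Stress test of Week 12 power**, with the same q applied to both endpoints. With one switcher in each arm (2.5%), IGA power is 85.4% if the scores are counted and 86.9% if scored as non-response. In the 10% cases, which go well beyond the likely exposure, it is 90.1% against 77.8% (secukinumab only) and 72.1% against 91.1% (placebo only). PASI 75 power stays above 99% throughout.

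**The case against.** The best defence is that this is a treatment-policy analysis: scores are used whatever happens after randomisation. The FAS follows intention to treat, SAP 1.1 places follow-up visits in the analysis periods, and Protocol 9.6 includes discontinuers' follow-up data in the Week 24 and Week 52 analyses. That choice would be legitimate. It is incomplete here for two reasons. The SAP never states it for switching. And the protocol lets switchers skip the remaining follow-up visits, so the data hold one post-switch score per patient rather than a continued record. The SAP also sets scores affected by the IRT dosing error to missing in one analysis (4.1), but has no counterpart for scores on a different drug. The extra sensitivity analyses in SAP 5.1.2.3 are conditional, unspecified, and tied in part to discontinuations other than for lack of efficacy.

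Several limits stand. All confirmatory hypotheses (H1 to H6) are at Week 12, comparison with placebo ends there, and no formal comparison with etanercept is planned. Discontinuers from induction are not mapped into maintenance, and the MI variable list shown for the primary endpoint stops at that week, so later switches cannot reach it. The end of SAP 2.6.4 is redacted, so a relevant rule there cannot be ruled out. Table 2-2b (etanercept windows) is not visible, so the day arithmetic is established only for secukinumab and placebo.

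A reader might infer that the Week 12 result is inflated in favour of secukinumab, or that the curves are off by 10 points. The documents support neither. Placebo switching lowers the Week 12 contrast, equal switching leaves it unchanged, and 10 points needs four switchers all responding in one window.

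**Conclusion.** The gap is real on the visible text: observed scores on another systemic drug are credited to the randomised arm, and neither imputation method deals with them. It bears mainly on the secondary by-visit estimates from Week 16 to Week 52. There each switcher normally contributes one observed score, each switched responder is worth 2.5 points in an arm of 40, and under MI the effect can extend to later visits. At Week 12 the likely exposure is 0 to 1 patient per arm, which does not call the confirmatory conclusions into question.

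This rests on assumptions the documents cannot settle: 1 to 4 switchers per arm of 40 before Week 52, some response on the new drug, and no covering rule in the redacted text.

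**What to change.** In SAP 2.6.4 and 2.6.5:

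- State that PASI and IGA values on or after the start of another systemic anti-psoriatic treatment, following discontinuation of study drug, are scored as non-response from that visit on in the pure non-responder analysis.
- Add an MI version that leaves those values out of the MI input and scores those visits as non-response.
- Show the as-observed analysis alongside, and report the number of affected patients by arm and visit.
- Label this as supportive for Week 12. The current SAP (December 2020) postdates the Week 24 lock, so re-scoring the primary analysis now would be post hoc.
- Do not extend the rule to every Table 5-2 treatment. Protocol 5.5.8 lets patients continue in the study once they stop a prohibited treatment, which is a different situation.

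The cost is a few lines of SAP text and one flag built from concomitant medication dates, which are already collected in follow-up (Table 6-2). Response rates may fall slightly.

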### **2.1.1.6 Multiple assessment within visit windows**

When there are *multiple assessments* in a particular visit window, the following rules are applied to select one value “representing” the subject in summary statistics in a visit window (See [Table 2-3](#)).

For baseline assessment definition see [Section 2.1.1.3](#). For post-baseline visit windows the following applies (unless otherwise specified):

- for *quantitative variables*, the *closest* to the actual visit will be chosen (if two assessments have the same distance, then the earlier one will be chosen);
- for *qualitative variables*, the *worst* record will be selected. It is noted that in the analyses performed, *worst* case will be always well defined (e.g., for urine protein values “+” and “++”, the worst case will be defined as “++”),
- in case qualitative variables are based on quantitative variables, e.g. PASI 75 response, the visit will be assigned to the quantitative variable, and this visit will be used for the derived qualitative variable.

